10.3 Participant recruitment

Patients undergoing planned left side heart valve surgery will be invited to participate. All potential participants will be sent or given an invitation letter and PIL (approved by the local Research Ethics Committee (REC)) describing the study. The patient will have time to read the PIL and to discuss their participation with others outside the research team (e.g. relatives or friends) if they wish. Most patients will have at least 24 hours to consider whether to participate. In a few cases, this time interval may be as little as 12 hours, for example for patients admitted for urgent planned surgery without prior notification to the waiting list co-ordinator. Despite the short notice, it is important to include these patients for the applicability of the trial findings since about 40% of patients having cardiac surgery are admitted as urgent cases.

Potential participants will be identified and approached with information about the trial prior to their surgery. An initial eligibility check will be performed prior to giving any details about the trial to the patient.

Formatte

Potential participants will be seen or contacted by a member of the local research team who will answer any questions and take informed consent if the patient decides to participate. Consent will be obtained either by face to face at a clinic appointment or remotely by telephone/video call or electronically using a purposed designed electronic database. The consent process will be described in detail in the study manual.

Details of all patients approached for the trial and reason(s) for non-participation (e.g. reason for ineligibility or patient decline) will be documented. Participant eligibility will be assessed in full as close to randomisation as possible.

10.4 Discontinuation/withdrawal of participants

Each participant has the right to withdraw at any time.

Withdrawals during treatment should not occur due to the nature and duration of the intervention; the duration of the intervention is from before cannulation for CPB and continued until 10 minutes post-CPB. However, a clinician may withdraw a participant at any time if they feel it is in the participant's best interests.

Participants withdrawn from their allocated intervention but willing to continue completing followup schedules will be encouraged to do so. If a participant withdraws, data collected up until that point will be included in the analyses.

Reasons for all discontinuations and withdrawals will be captured in the study database and reported.

10.5 Frequency and duration of follow up

After discharge from hospital, participants are followed up at three months after surgery. Data concerning health status will be collected by questionnaires.

10.6 Likely rate of loss to follow-up

Until discharge from hospital, the only losses to follow-up will be due to death or participant withdrawal; these losses are expected to be very few (<2%). We expect loss to follow-up at three months to be minimal (less than 5%); the Titre-2 trial (which randomised over 2000 cardiac surgery patients across 16 centres), achieved >95% follow-up to three months (34).

10.7 Expenses

Any documents that need to be returned by the participant will be given with a pre-paid envelope, so that no expenses are incurred.

If the post-operative DW MRI brain cannot be completed before discharge but the participant is willing to return within the 2-10 day timeframe to undergo the scan, then participants may claim for travel expenses. However, every attempt must be made to complete the DW MRI before the patient is discharged.

The CO2 study Protocol Version 6.0

11. Statistics

11.1 Sample size calculation

11.1.1 Main trial

The target sample size is 704 participants, 352 per group, which will provide 90% power at a 5% significance level (2-sided) to detect a 25% relative reduction in the incidence of post-operative cerebral infarcts with CDI, assuming a 48% rate in the placebo group. Missing data for the primary outcome is expected to be minimal as the DW MRI brain and assessment of stroke will be completed prior to the participant's discharge home.

Data from our systematic review and meta-analysis (21) showed a 43% relative risk (from 21% to 12%) reduction in the incidence of neurocognitive decline with CDI. It also showed a 47% relative risk reduction in the incidence of stroke over time following the introduction of CDI in Bristol in 2006 from 3.4% in 2005 to 1.6% in 2008. This was estimated from research data on 1754 valve surgeries and 42 strokes. This provided the basis for the target effect size; it is less than the effect observed in our systematic review, which is likely to have overestimated the treatment effect based on small RCTs at unclear or high risk of bias.

The anticipated event rate in the placebo group was chosen based on a meta-analysis of all available observational studies where brain MRI was routinely performed early after open heart valve surgery. Eight studies were identified with sample sizes ranging from 15 to 129 participants and rates of new ischemic lesions at MRI ranging from 38% to 72%. The pooled random effects estimate of new ischemic lesions was 55% (95% CI 48% to 63%). Assuming a 48% event rate (the lower limit of the 95% CI) leads to a larger sample size (compared to assuming a 55% event rate).

11.1.2 Mechanistic sub-study

There are no previous studies investigating the association between embolic load and brain injury post-cardiac surgery, but embolic load detected by TCD shows a strong correlation with DWI positive lesions (r=0.70) during coil embolization of unruptured intracranial aneurysms (35). Assuming a weaker association during open heart surgery the sample size for sub-study has been set at 100 participants which will provide 90% power at a 5% significance level (2-sided) to detect a correlation of 0.32 (linear regression r-squared of 0.1).

11.2 Stopping rules (phase 1)

There are three conditions that might lead the Trial Steering Committee (TSC) to recommend stopping the trial early:

- 1. A failure to recruit sufficient patients to meet the target sample size within the proposed duration of the grant and refusal of the funder to extend the duration of recruitment
- 2. A failure to deliver the intervention as allocated

3. A failure to complete the MRI scan according to the protocol before discharge after surgery

With respect to 1., it is planned to recruit the target sample size of 704 randomised participants over 24 months. NIHR-EME will formally review progress against this target after six months of recruitment, with the option of a contract break to minimise financial risk to the NIHR if recruitment does not reach a predefined criterion. After six months of active recruitment 92 participants should have been recruited, if the target recruitment rate is being met. Accepting recruitment typically starts slowly and increases over time as the trial gets established and that there is some variability from one month to the next (e.g. recruitment is typically lower over Christmas and in the summer holiday period than at other times of year). Therefore, it is proposed that trial recruitment will be halted if;

- a) fewer than 69 have been recruited within six months and
- b) we are unable to provide a plan that satisfies the NIHR-EME to make up the shortfall of 23 participants (i.e. the target recruitment of 4-5 participants per centre per month is not being exceeded and all eligible surgeons are participating)

The BTC CTEU will prepare a report for the Trial Steering Committee (TSC) to consider and make a recommendation to the NIHR-EME.

With respect to 2. and 3., the BTC CTEU will monitor adherence to the protocol throughout the trial and will investigate all cases of non-adherence. The BTC CTEU will prepare a report for the TSC to consider and propose halting the trial if the reasons for non-adherence cannot be addressed satisfactorily.

In addition to monitoring recruitment and adherence, the Data Monitoring and Safety Committee (DMSC) will monitor safety outcomes and the assumptions underpinning the sample size calculation (i.e. the event rate in the placebo group). The DMSC may recommend stopping the trial if the accrued data suggest that the trial is unsafe for one or both groups of participants or that a study of 704 participants will be inadequate, and a larger trial is not feasible.

11.3 Plan of analysis – primary and secondary outcomes

Analyses will be performed on the intention-to-treat basis and will be directed by a pre-specified statistical analysis plan. Analyses will use data from all patients randomised. Primary and secondary outcomes will be compared using logistic (binary variables), poisson (count variables), Cox proportional hazards (time to event variables), or linear mixed model (continuous variables measured at multiple time points) regression, with placebo as the reference group. Mixed models allow all participants with data to be included in the analysis, i.e. partial missing data (assumed missing at random) is permitted. Interactions between treatment and time will be examined and if significant at the 10% level, results will be reported separately for each post-operative time point; otherwise overall treatment effects will be reported. Model validity will be checked using standard methods; if a model is a poor fit, alternative models or transformations will be explored. Outcomes analysed on a logarithmic scale were transformed

back to the original scale after analysis and results presented as geometric mean ratios. Analyses will be adjusted for baseline values, and stratification variables (centre and type of surgery). Findings will be reported as effect sizes with 95% CIs.

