2.2 Magnetic resonance imaging (MRI) to detect perioperative brain injury

MRI examination of the brain is the "gold standard" for identifying and quantifying peri-operative brain injury (8) and has been used widely in randomised controlled trials (RCTs) investigating neuroprotective interventions in cardiac surgery (9-11). A variety of imaging techniques are applied to identify markers of such injury, including diffusion weighted imaging (DWI). The main advantage of DWI is that lesions typically appear within 2 hours of surgery and disappear after two weeks, therefore, new acute lesions represent "new" injury, so a baseline scan is not required to confirm that the lesion was not present before surgery. Another advantage is that the new framework for defining stroke proposed by the American Heart Association/American Stroke Association (8) includes neuroimaging (together with clinical or pathological evidence), so lesions found on DWI count as "silent" brain injury even in the absence of obvious clinical findings.

DWI lesions following left heart valve surgery are reported in about 50% of patients (5, 9). These lesions are multiple and very small (1-10mm in diameter and 32-750mm³ in volume). They are located in all cerebrovascular territories, but more frequently in frontal and watershed border zones and the pattern of distribution confirms an embolic basis. Few (\sim 9%) are associated with overt clinical signs of stroke so they represent "silent" brain injury in most cases (5, 9).

In population-based studies, a strong association has been found between "silent" brain injury identified by MRI and prevalent cognitive dysfunction and dementia (12-14), therefore it is plausible that a similar relationship exists between the appearance of new lesions after cardiac surgery and neurocognitive decline. Some preliminary data has suggested that the appearance of new "silent" brain lesions after cardiac surgery is associated with early post-operative

neurocognitive deterioration (15) although further investigations with longer follow-up are needed.

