5.1.2 Secondary outcomes

Data will be collected to characterise the following secondary outcomes:

- 1. Number and volume of DWI brain lesions
- 2. Objective quantification of the impairment caused by new ischemic brain injury assessed using the National Institutes of Health Stroke Scale (NIHSS)
- 3. Delirium assessed using the 3-minute diagnostic interview for Confusion Assessment Method (CAM)
- 4. Functional status assessed using the Barthel Index score
- 5. Neurocognitive function in 6 domains (verbal memory, visual memory, executive functioning, visuospatial or constructional praxis, attention, and information processing speed), assessed using the following tests:
 - a. Addenbrooke's Cognitive Examination III (ACE III)
 - b. Oral Trail making Tests A and B (oTMT A&B)
- 6. Quality of life assessed using the physical and mental subscales of the 12-Item Short-Form Health Survey (SF-12)
- 7. Composite of all-cause mortality, clinical stroke, or acute kidney injury within 30 days of surgery
- 8. Serious adverse events (SAEs) to 3 months
- 9. Survival to 3 months

All patients will be consented for passive follow up for up to five years after their surgery from NHS and national health and registration records to determine any association between silent brain lesions and long-term neurological outcomes (e.g. dementia).

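### Section 11.3 names Poisson regression for counts with no provision for overdispersion, although the protocol's own description of DWI lesions makes overdispersion likely

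*Protocol*

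**What the plan says.** Section 11.3 assigns model families by variable type: outcomes will be "compared using logistic (binary variables), poisson (count variables"), with Cox regression for times to event and a linear mixed model for continuous variables measured repeatedly. It names no variance estimator and does not mention overdispersion or excess zeros. It adds two safeguards. The analyses "will be directed by a pre-specified statistical analysis plan", and "Model validity will be checked using standard methods; if a model is a poor fit, alternative models or transformations will be explored".

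The count outcome is in section 5.1.2, where the first secondary outcome is "Number and volume of DWI brain lesions". Two places describe how it should be distributed. Section 2.2 says "DWI lesions following left heart valve surgery are reported in about 50% of patients" and then "These lesions are multiple and very small". Section 11.1.1 sizes the trial "assuming a 48% rate in the placebo group", a rate taken from a meta-analysis of new ischaemic lesions on MRI. No section gives a mean, standard deviation or distribution of lesions per patient.

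**The concern.** A Poisson distribution has one parameter, so the share of patients with no lesion fixes the mean, the variance and the share with several lesions. About half zeros together with multiple lesions in the rest is the usual signature of overdispersion, where the variance exceeds the mean. Poisson regression still estimates the rate ratio consistently in that case, but its model-based standard error is too small. The confidence interval for the effect on lesion count would then be too narrow, and a chance difference in lesion burden would be declared significant too often.

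This can be foreseen from the protocol itself. If it is left to the fit check, the replacement will be picked once the outcome data are available, among candidates that need not agree.

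**Working it through.** **Inputs.** Placebo event rate 48%, relative reduction 25%, 352 per group, two-sided 5%, 90% power (section 11.1.1). About 50% of patients with lesions, described as multiple (section 2.2). I take the 48% as the share with at least one DWI lesion, since it comes from MRI lesion studies. The mean number of lesions per positive patient, m, is assumed to be 2, 3 or 5.

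**The plan's own figure.** For 48% against 36% the average is 0.42. The pooled formula gives n = [1.96·√(2·0.42·0.58) + 1.282·√(0.48·0.52 + 0.36·0.64)]² / 0.12² = (1.368 + 0.888)² / 0.0144 ≈ 354 per arm. Power at 352 is 89.9%. The stated sample size reproduces and does not depend on the count model.

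**What a Poisson with 52% zeros implies.**
- Mean: λ = −ln(0.52) = 0.654.
- Mean among positives: 0.654 / 0.48 = 1.36.
- Exactly one lesion among positives: 0.654 × 0.52 / 0.48 = 71%, so two or more in 29%.
- With 50% zeros, the figures are 1.39 and 31%.
- Across the 38% to 72% positive reported by the source studies, the share of positives with two or more runs from 22% to 51%.
- In reverse: if positives average 3 lesions, the overall mean is 0.48 × 3 = 1.44, and a Poisson would predict exp(−1.44) = 24% zeros, not 52%.

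**Effect on the test.** With 48% positive, the variance-to-mean ratio (VMR) depends on the shape among positives:
- all positives equal to m: VMR = 0.52m
- 1 plus a Poisson with mean m − 1: VMR = (m − 1)/m + 0.52m
- geometric: VMR = (2m − 1) − 0.48m
- a single negative binomial with 52% zeros and the same overall mean: solved numerically

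Under no treatment effect, the model-based Poisson test has type I error of about 2·[1 − Φ(1.96/√VMR)].

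| Mean per positive (assumed) | Equal: VMR, error | 1 + Poisson: VMR, error | Geometric: VMR, error | Negative binomial: VMR, error |
|---|---|---|---|---|
| 2 | 1.04, 5.5% | 1.54, 11% | 2.04, 17% | 2.06, 17% |
| 3 | 1.56, 12% | 2.23, 19% | 3.56, 30% | 4.12, 33% |
| 5 | 2.60, 22% | 3.40, 29% | 6.60, 45% | 9.11, 52% |

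Simulation with 352 per arm and no covariates agrees for the first three shapes: about 4-18%, 11-32% and 21-44% at means of 2, 3 and 5. A robust variance held the error at about 4-6% in the same data.

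**Would the fit check notice?** In 2,000 simulated trials per mean with negative binomial data, a Pearson goodness-of-fit test flagged the misfit every time. Where positives are nearly identical and the mean is 2, the VMR is close to 1 and such a test would often pass, but there is then almost no inflation either.

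**The case against.** The strongest reply is that section 11.3 is a generic list and not a final model for lesion count. It requires a fit check, allows alternatives and defers to a statistical analysis plan that is not shown. The error rates above describe a Poisson test with model-based standard errors and no check, which is not the procedure as written. Naming Poisson regression does not exclude a robust variance either. All of this stands, and three stronger readings should not be drawn.

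- A reader might infer that the protocol fixes an invalid analysis. It does not, because the check and the deferral are both stated.
- A reader might infer that the protocol's figures rule out a Poisson distribution. They do not. Multiple is a qualitative word, no mean is given, and 48% is deliberately the lower confidence limit of a pooled 55%. At 72% positive a Poisson would put two or more lesions in about half of the positives.
- A reader might infer that lesion volume has no workable analysis, or would be compared only in lesion-positive patients. No section says so. The sentence that ends "back to the original scale after analysis and results presented as geometric mean ratios" applies to outcomes analysed on a log scale and does not say that volume is one of them. Section 11.3 says data from all randomised patients are used.

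The reply does not remove one point. The named method is likely to fail its own check for a reason visible now, and nothing names its successor. A statistical analysis plan that specified plain Poisson would comply with the protocol.

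**Conclusion.** The point holds as a cheap improvement to a secondary analysis. A Poisson model without provision for overdispersion is hard to reconcile with about half the patients having no lesion and the rest having multiple lesions. The size of the problem is uncertain. If model-based standard errors were used, the type I error would be about 4-18%, 11-32% or 21-44% at assumed means of 2, 3 or 5 lesions per positive patient, and up to about 52% under a negative binomial at a mean of 5. These figures rest on the assumed means and shapes, 48% positive, 352 per arm and no covariates. The fit check makes an uncorrected error of that size unlikely. What remains is a replacement model chosen after the data are seen.

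Lesion volume is a secondary note, not an error. It comes from one scan and is zero in about half the patients, so no listed family fits it directly. The primary logistic analysis and the sample size are not affected.

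**What to change.** In section 11.3, replace the Poisson entry for count variables by one pre-specified method that tolerates overdispersion, and make it the main analysis of lesion count. Poisson regression with robust standard errors is the smallest change and keeps the rate ratio; negative binomial regression is also acceptable. Choose one before any comparative look at the data.

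For lesion volume, the statistical analysis plan should name one method that uses all scanned patients, zeros included, for example proportional-odds regression or a stratified rank test with zero as the lowest value.

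The cost is wording only, with no change to data collection or sample size. The interval for lesion count becomes wider than the model-based Poisson interval by about √VMR: at an assumed mean of 3, √1.56 = 1.25 to √4.12 = 2.03 times. That width reflects the real uncertainty. If an ordinal or rank method is chosen for volume, its effect will be reported on that scale.

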The use of post-operative cognitive dysfunction as a marker of peri-operative brain injury is problematic because of potential difficulties in ascertainment (5). Multiple factors affect neurocognitive test performance during the first week after surgery; namely treatment of post-operative pain, sedation, and other clinical recovery issues. Many, if not most, patients have some degree of cognitive dysfunction in the immediate post-operative period. Such a nearly universal occurrence is clearly not an appropriate marker of brain injury. Only after this period has passed can an objective assessment of the patient's cognition be performed; although the duration of altered cognition after surgery has not been defined clearly (5).

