6.8 Research procedures

Participants will be required to do, or undergo, the following tasks or investigations specifically for the study which are also outlined in table 1.

Pre-surgery:

- Read the CO2 study PIL (can be sent to the patient's home before the patient attends the hospital for their surgery)
- Provide informed consent to participate, if willing to do so
- Assessment of NIHSS, CAM, functional status (Barthel Index) and neurocognitive function (ACE III and TMT A&B)
 Complete quality of life questionnaire (SF-12)

During surgery:

- Receive the intervention allocated at randomisation during open heart valve surgery
- If participating in the mechanistic sub-study (Bristol centre only), a transcranial doppler ultrasound of the middle cerebral artery and near infrared spectroscopy of the frontal lobe will be conducted during surgery
- Assessment and reporting of any AEs and SAEs experienced

Post-surgery inpatient stay:

- Day 3 (between 3-5 days post-surgery): Assessment of NIHSS and CAM
- DW MRI brain scan ideally between 2 and 7, but no more than 10, days after surgery before hospital discharge
- Assessment and reporting of any AEs and SAEs experienced

Post-discharge:

Three months post-surgery (conducted remotely): Assessment of NIHSS, CAM, functional status (Barthel Index) and neurocognitive function (ACE III and TMT A&B) Complete quality of life questionnaire (SF-12).

Collection and assessment of any SAEs experienced after discharge from hospital

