6.8.1 Neurocognitive function

Neurocognitive function tests, assessing six domains; visual and verbal memory, executive functioning, visuospatial or constructional praxis, attention and information processing speed, will be performed by a member of the research team who has undergone suitable training.

The tests to assess neurocognitive function are:

- Addenbrooke's Cognitive Examination III (28)
- Oral trail making test part A and B (29, 30)

Tests will be performed prior to surgery and at three-month follow up and should take around 30 minutes to conduct.

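### A 10% treatment-by-time interaction test decides whether NIHSS, and possibly CAM delirium, is reported at day 3 and 3 months or only as one overall effect

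*Protocol*

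**What the plan says.** Section 11.3 of the protocol assigns repeated continuous outcomes to a "linear mixed model (continuous variables measured at multiple time points) regression, with placebo as the reference group". Shortly afterwards it sets a reporting rule that hangs on the treatment-by-time interaction: "if significant at the 10% level, results will be reported separately for each post-operative time point; otherwise overall treatment effects will be reported". The rule is stated without exceptions.

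Section 6.8 and Table 1 show where it can apply. The early visit is "Day 3 (between 3-5 days post-surgery): Assessment of NIHSS and CAM", and both instruments are repeated at three months. The Barthel Index, ACE III, oral Trail Making Tests and SF-12 have one post-operative assessment each; of the neurocognitive tests, section 6.8.1 says "Tests will be performed prior to surgery and at three-month follow up". The rule can therefore matter only for NIHSS and CAM. Section 5.1.2 lists both as secondary outcomes and names no principal time point for either.

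**The concern.** The interaction test chooses which quantity is reported: two time-specific effects or one overall effect. When it is not significant, the plan commits only to the overall effect. Non-significance may simply reflect low power, and the protocol states no power for this test.

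Carbon dioxide insufflation acts during the operation, so an effect visible at days 3 to 5 and gone by three months is a plausible pattern. Under that pattern the overall effect understates the early one, and a reader of the results may never see the day 3 estimate. No principal time point is named that would guarantee its reporting.

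**Working it through.** **The protocol's own figure.** Section 11.1.1 gives 352 per group for 48% versus 36% (a 25% relative reduction), two-sided 5%, 90% power. Unpooled formula: n = (1.960 + 1.282)² × (0.48×0.52 + 0.36×0.64) / 0.12² = 10.507 × 0.480 / 0.0144 ≈ 350.2, so 351 per group (702). The pooled-variance version gives 354 per group (708), and power at 352 per group is 89.9%. The figure reproduces, and 352 per arm is used below.

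**Inputs that the protocol does not give (assumptions).** Normal outcome with equal variance at both times; true effect d (in SD) at day 3 and zero at three months; within-patient correlation ρ.

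**Formulas.**
- SE at one time = √(2/352) = 0.0754.
- SE of the interaction = 0.0754 × √(2(1−ρ)): 0.0892 at ρ = 0.3, 0.0754 at ρ = 0.5.
- SE of the overall effect = 0.0754 × √((1+ρ)/2): 0.0608 and 0.0653.
- Overall effect = (d + 0)/2 = d/2.
- Pooled when |interaction estimate| / SE < 1.645.

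Example, d = 0.20, ρ = 0.3: 0.20/0.0892 = 2.24. The chance of significance at 10% is P(Z > 1.645 − 2.24) = 72.5%, so pooling occurs in 27.5% of trials.

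Coverage comes from simulating the two-stage rule with 400,000 draws per row. The third column scores whichever interval is reported against the day 3 effect.

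| d | ρ | Pooled | Day 3 coverage, whole procedure | Day 3 coverage when pooled |
|---|---|---|---|---|
| 0.15 | 0.3 | 48% | 86% | 77% |
| 0.15 | 0.5 | 37% | 90% | 79% |
| 0.20 | 0.3 | 28% | 87% | 62% |
| 0.20 | 0.5 | 16% | 91% | 67% |
| 0.20 | 0.7 | 4% | 94% | 70% |
| 0.25 | 0.5 | 5% | 93% | 52% |

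At d = 0.25 and ρ = 0.7, pooling occurs in 0.4% of trials. In every row the mean pooled estimate is d/2. With 335 per group (section 10.6 expects less than 5% loss at three months), the first four pooling figures become 50%, 38%, 29% and 17%.

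**Delirium, if the rule covers it.** Assume 20% versus 13% at day 3, 1% or 2% in both arms at three months, and independent occasions. (Section 2.1 cites more than 20% in patients over 65; the other rates are assumptions.)
- Day 3 log odds ratio = ln(0.13/0.87) − ln(0.20/0.80) = −0.515, OR 0.60. Variance = 1/(352×0.20×0.80) + 1/(352×0.13×0.87) = 0.0429.
- Three-month variance = 2/(352×0.02×0.98) = 0.290 at 2%, and 0.574 at 1%.
- Interaction z at 2% = 0.515/√(0.0429 + 0.290) = 0.89, significant at 10% in about 23% of trials. At 1%: z = 0.66, about 17%.
- Inverse-variance weight on day 3 at 2% = 0.290/(0.290 + 0.0429) = 0.87. Pooled OR = exp(−0.515 × 0.87) = 0.64. At 1% the weight is 0.93 and the pooled OR is 0.62.
- When pooled, the interval covers the day 3 OR in 94% to 95% of trials.

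For 15% versus 10%, the OR of 0.63 becomes 0.66 to 0.68, with the same coverage. With few late events the interaction test has little power, but the pooled estimate is almost wholly the day 3 estimate. Dilution grows if late delirium is common: at 5% in both arms, 0.60 becomes 0.69 and coverage when pooled is 88%.

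**The case against.** The rule is pre-specified, 10% is a lenient threshold, and nothing forbids a descriptive table by time point. The interval for the overall effect covers the overall effect at 95%; its coverage is poor only when scored against the day 3 effect, which it does not claim to estimate. That is correct. What remains is that the plan does not commit to reporting the day 3 effect and lets the data settle whether it appears.

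The normal model may suit NIHSS badly. Section 2.1 puts stroke at 2% to 6%, and section 2.2 says few lesions (about 9%) come with overt signs, so most scores are likely to be near zero. Section 11.3 also allows other models when fit is poor. The table is therefore an illustration, not a forecast, and the halving depends on equal variances.

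The interaction sentence follows the text on mixed models for continuous outcomes, and no repeated-measures model is named for binary ones. Whether it governs CAM is open.

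A reader might also infer that the protocol itself treats the first week as a separate question, because section 2.2 says "Only after this period has passed can an objective assessment of the patient's cognition be performed". That passage explains why early neurocognitive testing is a poor marker of brain injury. Those tests have a single post-operative time point, so the rule never reaches them, and the passage does not discuss NIHSS or CAM.

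**Conclusion.** The point stands as a minor one, limited to NIHSS and, if the sentence extends to binary outcomes, CAM delirium. The primary outcome is a single binary event within 10 days and is not touched.

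For a continuous outcome with a day-3-only effect of 0.15 to 0.20 SD and correlation 0.3 to 0.5, only a halved effect would be reported in about 16% to 48% of trials. The problem nearly vanishes with larger effects or higher correlation. All of this rests on assumed effect sizes, correlations and normality.

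Two stronger readings are tempting and not supported. One is that a real delirium effect would be halved: with few three-month events, an odds ratio of 0.60 moves only to 0.62 to 0.64, and the actual loss is that the day 3 result usually goes unreported on its own. The other is that the protocol takes non-significance as demonstrating equal effects, or that the average is meaningless. It says neither of the first, and whether an average is useful is a matter of judgement. The defect is that the average may replace the time-specific results.

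**What to change.** Replace the conditional sentence in section 11.3, and carry the change into the SAP: for outcomes assessed at day 3 and three months, always report the treatment effect with its 95% CI at each time from the same model, and give the interaction p-value as descriptive information. An overall effect may be added but does not replace them. State explicitly whether this applies to CAM as well as NIHSS.

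The cost is one sentence and two estimates per outcome instead of one, with no new data. The time-specific intervals are somewhat wider than a pooled one: under the assumptions above, SE 0.0754 against 0.0608 to 0.0653.
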